CDR	Data Collection Notebook
051	Committee on the Ethics of Research with Medicinal
CEIM	Products
IC	Confidence interval
CI	Informed consent
CTCAE	Common Toxicity Criteria for NCI Adverse Event
Cro	Contract research organisation
DRS-R-98	Delirium Rate Scale-Revised-98
DSM IV	Diagnostic and Statistical Manual of Mental Disorders
EVA	Visual Analog Scale
GBPC	Good Clinical Practice Guide
IBSAL	Biomedical Research Institute of Salamanca
Ме	Resident Intern
NCI	National Cancer Institute
p.e.	For example
PCR	C-reactive protein
BAO	Serious and Unexpected Adverse
RAGI	Reaction
RASS	Richmond Agitation sedation Scale
REec	Spanish Registry of Clinical Studies
SF-36	Health-Related Quality of Life Questionnaire
SNC	Central nervous system

1. SUMMARY AND GENERAL INFORMATION

1.1TYPE OF APPLICATION

Non-commercial low-intervention clinical trial

1.2IDENTIFICATION OF THE PROMOTER

Fundación Instituto de Estudios Ciencias de la Salud de Castilla y León (IECSCYL)- Instituto de Investigación Biomédica de Salamanca (IBSAL).

IECSCYL-IBSAL Foundation.

1.3TITLE OF THE CLINICAL TRIAL Randomized, double-blind, controlled clinical trial for quetiapine prophylaxis of postoperative delirium in at-risk surgical patients.

1.4PROTOCOL CODE

QUEPRO

1.5COORDINATING AND PRINCIPAL INVESTIGATOR [name]. Anesthesia, rehabilitation and pain treatment service. C.A.U.S.A

1.6CENTRES WHERE THE STUDY IS PLANNED University Assistance Complex of Salamanca

1.7CEIM Committee on Research Ethics with medicines Salamanca Health Area

1.8RESPONSIBLE FOR MONITORING Monitor: [name] Coordinator in the Promoter: [name]. Clinical Trials Area. IBSAL

RESPONSIBLE FOR PHARMACOVIGILANCE: [name] (UICEC H. Universitario de Canarias)

1.9.DESCRIPTIONOF STUDY PRODUCTS. Experimental treatment and control

Quetiapina (experimental) vs placebo (control)

Route of administration: oral

Experimental: quetiapine 25 mg gelatin capsule-coated tablets. Cada tablet contains 25 mg of q uetiapina (as quetiapine fumarate). Excipient: lactose 18.5 mg

Therapeutic group: N05A H04. Antipsychotics: diazepines, oxacepines and thiazepines.

Anatomical Group: (N) Nervous system

Placebo: gelatin capsule.

1.10 CLINICAL TRIAL PHASE Phase III

10.110BJECTIVES

Main: to know the incidence of postoperative delirium in patients at risk, over 65 years of age, treated early with prophylactic quetiapine compared to those treated with placebo.

Side:

- 1. Evaluate the safety and tolerability of the medication applied
- 2. To compare the efficacy of medication versus placebo in relation to:
 - length of hospital stay
 - perceived quality of life
 - all-cause mortality at discharge and 28±2 days from initiation (1st dose) of quetiapine treatment.
- 3 In cases where delirium develops, know:
 - Time of appearance
 - the duration and severity of the same
 - Total dose of treatment with other antipsychotics.

1.12STUDY DESIGN

Prospective low-level non-commercial, balanced, randomized, double-blind clinical trial (phase III) clinical trial.

1.13STUDY DISEASE

Delirium developed during the period after surgery.

Delirium is an acute alteration of consciousness accompanied by inattention, disorganization of thought and alterations of perception that fluctuate in a short period of time (DSM IV). It is one of the most frequent complications of surgery and develops characteristically between 0-96 h after the intervention. It is associated with worse prognosis in the short and long term.

1.14STUDY VARIABLES

- A. The main variable is the proportion of patients diagnosed with delirium (number of delirium cases/total number of patients) in the first 4 postoperative days in both branches.
- B. Secondary variables:
 - 1. number of days from the start of treatment to the onset of delirium, if it appears,
 - 2. duration of delirium, in days,
 - 3. severity of delirium measured with validated scale (DRS-R-98)
 - 4. total dose (mg) haloperidol or another antipsychotic to control symptoms of delirium,
 - 5. Security variables:
 - degree of sedation: by RASS scale,
 - QTc prolongation: increase in mseg on the control ECG.
 - presence or absence of extrapyramidal symptoms (tremor, involuntary movements, stiffness)
 - 6. days of hospital stay since surgery,

- 7. perceived quality of life (through SF36 validated questionnaire) 28±2 days after initiation of treatment,
- 8. All-cause mortality at discharge and 28±2 days after initiation of treatment

1.15STUDY POPULATION AND TOTAL NUMBER OF PATIENTS

Patients older than or equal to 65 years of age who are going to undergo major non-cardiac surgery and who have a score equal to or greater than 5 on the Delphi scale:

- Age: 70-79 years: 1 point; >80 years: 2 points
- Physical activity: need for assistance, not self-sufficient: 2 pointss
- Alcoholism: 1 point
- Hearing deficit: 1 point
- History of delirium: 2 points
- Urgent surgery: 1 point
- Non-laparoscopic surgery: 2 points
- Admission to Critical Care Units: 3 points
- C-Reactive Protein (CRP) value > 10 mg/dL: 1 point

The necessary sample size will be 350 patients, 175 patients per branch (control and experiment).

1.16DURATION OF PROCESSING

The duration of the treatment will be three days included in the early postoperative phase. Quetiapine will be administered orally to the patients of the experimental group 60 minutes after arrival at Resuscitation/Post-Anesthetic Recovery Unit and thereafter every 12 hours until the 3rd postoperative day. Subjects in the control group will be given placebo in the same time and form as subjects in the experimental group.

1.17 CLINICAL TRIAL SCHEDULE.

The total duration of the clinical trial will be approximately 3 years. They include the period for approvals and coordination of the project, period of recruitment and monitoring, period or analysis of results and a final period for the publication of results.

1.18COLLABORATING INVESTIGATORS OF THE TRIAL

[name] [name]. Head of Service Anesthesiology, resuscitation and pain management. C.A.U.S.A - Biomedical Research Institute of Salamanca (IBSAL)

[name] [name]. Medical assistant to the Anesthesiology, Resuscitation and Pain Treatment Service. C.A.U.S.A. - Biomedical Research Institute of Salamanca (IBSAL).

[name] [name]. Medical assistant to the Anesthesiology, Resuscitation and Pain Treatment Service. C.A.U.S.A.

[name] [name]. Medical assistant to the Anesthesiology, Resuscitation and Pain Treatment Service. C.A.U.S.A.

[name] [name]. Head of section of the Anesthesiology, Resuscitation and Pain Treatment Service. C.A.U.S.A.

[name] [name]. Medical assistant to the Anesthesiology, Resuscitation and Pain Treatment Service. C.A.U.S.A.

[name]. Medical assistant to the Anesthesiology, Resuscitation and Pain Treatment Service. C.A.U.S.A.

[name] [name]. Assistant Physician Anesthesiology, Resuscitation and Pain Treatment Service. C.A.U.S.A.

[name]. Medical assistant to the Anesthesiology, Resuscitation and Pain Treatment Service. C.A.U.S.A.

[name]. Medical assistant to the Anesthesiology, Resuscitation and Pain Treatment Service. C.A.U.S.A.

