3 JUSTIFICATION

According to the DSM-IV, delirium is an acute alteration of consciousness accompanied by inattention, disorganization of thought and alterations of perception that fluctuate in a short period of time. Postoperative delirium is one of the most common complications of surgery, with an incidence ranging from 10-51% in elderly patients at risk and up to 80% in those requiring critical care (1). It develops characteristically between 0 and 96 hours after the intervention (2) and is associated with a worse prognosis in the short and long term, with an increase in mortality and hospital stay and, therefore, an increase in economic expenses (3,4). The antipsychotic of choice for treatment is haloperidol (5,6), although its efficacy is limited in part by its side effects (mainly extrapyramidalism and prolongation of

the QTc interval) and lack of response in some patients. To solve these problems, second-generation or atypical antipsychotics appear, which have a more favorable safety profile with similar efficacy in clinical response (7). However, despite treatment, the prognosis does not seem to improve once delirium is triggered (4,8), so prophylaxis may be essential. Thus, although non-pharmacological prophylaxis measures (respect for wake-sleep cycle, pain control, early mobilization, providing visual and auditory aids...) have shown efficacy in reducing the incidence of delirium in this type of patients (4), this decrease is closely related to the complete follow-up of all measures, which implies a very important work overload without evidence of improvement in fundamental variables at discharge, such as functional or cognitive status (9). Therefore, pharmacological prophylaxis is gaining interest (4), although the evidence in the literature is limited. It seems logical to think that, just as antipsychotics are effective for the treatment of delirium, they will also be effective for pharmacological prophylaxis.

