In this regard, a number of studies with haloperidol and atypical antipsychotics have presented variable results, possibly related to the quality of the studies, variability in the tools used for the diagnosis of delirium and the selection of high-risk patients. The first large randomized clinical trial was conducted in 430 postoperative hip replacement patients. It failed to demonstrate a reduction in the incidence of delirium when 1.5 mg haloperidol was administered orally divided into three doses, but the severity and duration of delirium decreased (10). Larsen (11), in 2010, tested olanzapine 5 mg orally in 400 patients and managed to demonstrate that the risk of developing delirium in the intervention group was lower (RR 0.36, 95% CI 0.24 to 0.52), although episodes of delirium were longer lasting and severe. In 2014, Fukata (12) administered 121 patients 2.5 mg of intravenous haloperidol daily after general, trauma or other surgery, and could not demonstrate a decrease in the incidence of delirium in the intervention group. And yet, Wang (1), using haloperidol in patients undergoing noncardiac surgery, demonstrated clinically significant incidence decreases. Despite the risk of bias in these studies, there was no evidence of adverse effects with the use of these antipsychotics at low doses.

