We think that, within the group of atypical antipsychotics, quetiapine, due to its pharmacological profile (low affinity for dopamine receptors and μ receptors; high affinity for serotonergic receptors), could be useful in the prophylaxis of delirium and provide sedation without causing too many extrapyramidal effects (3) or precipitating acute episodes of delirium. In the current literature, there are no clinical trials with quetiapine for postoperative delirium prophylaxis but there are for the treatment of delirium. A series of randomized trials (7, 13,14) and one open-label trial (3) suggest that quetiapine may be effective and safe. Studies show faster resolution of symptoms than with placebo and find the same efficacy of other antipsychotics such as haloperidol, with low incidence of side effects, mainly drowsiness, without finding significant differences. The average dose used in these studies ranges from 40 mg to 200 mg, because they use increasing doses until symptoms are controlled. But there are studies that show efficacy with lower doses: 25-40 mg / day. They are studies carried out in the medical population and in critical care, and have certain limitations: n small, assessment of the effectiveness of treatment with quetiapine with different scales ... Even so, they would justify the use of quetiapine as prophylaxis at doses lower than those used for treatment. In this sense, there are two international clinical trials underway on postoperative delirium prophylaxis in the population at risk in critical care units, with an initial dose of quetiapine 12.5mg, in one of them adjusting for patient weight and the other with increasing doses as needed (15,16). Taking into account, in addition, that the clearance of the drug in patients over 65 years of age is decreased and, therefore, the half-life of the drug is extended in this population, we believe that the use of doses of quetiapine of 25 mg every 12 hours during the first three days of the postoperative period in patients at risk is justified.

One aspect to take into account is to determine the population at risk (in which we would suppose greater benefit of prophylactic measures), which can be complicated since until now there is no reliable

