4 HYPOTHESES AND OBJECTIVES

Hypothesis: The prophylactic administration of an antipsychotic with fewer side effects, such as quetiapine, in patients identified with a validated scale decreases the incidence of delirium during the postoperative period compared to placebo administration.

The main objective of the study is to determine the incidence of postoperative delirium in patients at risk, over 65 years of age, treated early with prophylactic quetiapine compared to those treated with placebo.

The secondary objectives are:

- eassess the safety and tolerability of the medication applied.
- cCompare the efficacy of medication versus placebo in relation to:
 - the length of hospital stay.
 - perceived quality of life at 28±2 days from the start (1st dose) of quetiapine treatment.
 - all-cause mortality at discharge and 28±2 days from initiation (1st dose) of quetiapine therapy.
- In cases where delirium develops, know:
 - Time of appearance.
 - the duration and severity of the same.
 - total treatment with other antipsychotics.

5 CLINICAL TRIAL DESIGN.

5.1 . DESCRIPTION OF VARIABLES

The main variable is the proportion of patients diagnosed with delirium (number of delirium cases/total number of patients) in the first 4 postoperative days. We will use a validated scale based on the DSM-IV definition of delirium, CAM: *Confusion Assessment Method* scale (17,24-27).

The secondary variables are:

- 1. Number of days from the start of treatment to the onset of delirium, if it appears.
- 2. duration of delirium, in days.
- 3. severity of theirium measured with validated scale (DRS-R-98).
- 4. D Total osis (mg) haloperidol or another antipsychotic tocontrol the symptoms of delirium.
- 5. Security Costs:
 - Sedation degree: using RASS scale.
 - QTc prolongation: increase in mseg in the control ECG.
 - presence or absence of extrapyramidal symptoms (tremor, involuntary movements, rigidity).
- 6. Days ofhospital stay of the surgical intervention.
- 7. perceived quality of life (through validated questionnaire SF36 or SF 12) 28±2 days after initiation of treatment.
- 8. mortality from all causes at discharge and 28±2 days after initiation of treatment.

Additional variables that will also be collected:

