- Basal cognitive function (valued with MINIMental o 6 ICT).
- CAM scale.
- ECG and QTc measurement.
- III. Postoperative visits: A daily personal clinical visit will be made to all randomized patients during the first four days of the postoperative period or during the duration of their admission if it is less than 4 days. In this case, the last visit during admission will be the visit to discharge.

These clinical visits will be listed in corresponding to the postoperative day: visit 1st day post, visit 2nd day post... so on until the 4th postoperative day.

Procedures to be performed:

- CAM scale.
- RASS scale.
- Extrapyramidal symptoms.
- vital signs.
- ECG and QTc measurement (after administration of the 4th dose).
- Complete laboratory tests (at least one during the first four days after surgery).
- VAS scale and analgesia received (opiates).

In addition, during the 1st postoperative visit, the intraoperative variables will be collected:

- Type of surgical intervention and specialty.
- urgent ly programmed.
- anesthetic technique performed.
- Drugs used, doses and routes of administration(benzodiazepines, opiates, glucocorticoids, atropine).
- Measurement of anesthetic depth and/or regional brain oxygen saturation where possible.
- Duration anesthesia .
- EVA upon admission to URPA/Resuscitation.
- Analgesia: IV or by regional techniques(drug used, dose and administration).
- blood transfusion.

If the patient develops delirium, the daily visit will continue until the clinic disappears. In this case, the following will also be collected:

- severity of the picture using DRS scale -R- 98
- Drug used for its treatment, dose and route of administration.

- IV. Discharge visit: when the patient meets criteria and is discharged. The following will be collected:
 - Reason for hospital discharge.
 - CAM.
 - RASS.
 - vital signs.
 - Extrapyramidal symptoms.
 - Hospital evolution including complications that have appeared and that have required medical treatment (≥ grade II Clavien-Dindo scale): blood transfusion, surgical reoperation, pneumonia
 - mortality.
 - complete anal itatic if it has not been collected in the postoperative visits.
 - If you have developed delirium:
 - × duration.
 - × Severity.
 - × Dosage and route of administration of the drug used for its treatment.

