7.3 CONCOMITANT AND PROHIBITED TREATMENTS

All types of anesthetic drugs and analgesic techniques are allowed according to the needs of each patient, and must be reflected in the data record book: the anesthetic technique performed, the anesthetic depth and regional brain oxygen saturation, if it has been possible to measure it, and the drugs used that in previous studies have been related to delirium (benzodiazepines, opiates, corticosteroids and atropine).

The use of drugs for adequate control of pain, heart rate and blood pressure is recommended as needed, including opioids and regional analgesic techniques, leaving the drug used recorded.

According to the Technical Label of the investigational medicinal product, concomitant administration of cytochrome P450 3A4 inhibitors, such as HIV protease inhibitors, azole-type antifungal agents, erythromycin, clarithromycin and nefazodone, is contraindicated.

Considering the main effects of quetiapine on the central nervous system, quetiapine should be used with caution in combination with other centrally acting drugs and alcohol.

In case of developing delirium, the usual treatment will be carried out not intervening in it, leaving reflected in the CRD drug used and dosage. In this case, if it develops during the first 3 days, the study medication will be discontinued .

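### The rescue-antipsychotic variable is one milligram total across different drugs, with no conversion or split by drug, so it mixes drug choice with treatment need

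*Combined protocol and SAP*

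**What the plan says.** Section 1.14 (B.4) lists as a secondary variable the "total dose (mg) haloperidol or another antipsychotic to control symptoms of delirium". Section 5.1 repeats it as a total in mg of "haloperidol or another antipsychotic tocontrol the symptoms of delirium". The matching objective in the synopsis applies to patients who develop delirium and is also a single total, over drugs in the plural: "Total dose of treatment with other antipsychotics".

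The rescue drug is not fixed. Under section 7.3, if delirium develops, "the usual treatment will be carried out not intervening in it, leaving reflected in the CRD drug used and dosage". Section 7.2 (postoperative visits) has the CRD capture "Drug used for its treatment, dose and route of administration".

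Section 10 does not mention this variable. It sends continuous variables in general to a t test or a Mann-Whitney test, two-sided at 5%. No section gives an equivalence unit, an analysis by drug, a rule for oral against intravenous dosing, or stratification by drug.

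**The concern.** A milligram measures the amount of one drug given by one route. Across antipsychotics of different potency it is not a common unit. A single total over whichever drug was used therefore carries two signals: how much treatment the delirium needed, and which drug the treating physician chose. Only the first is of interest when the arms are compared.

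The number of delirium cases will be small, so the comparison has little precision to lose. Variation from drug choice can hide a real difference in need. If the drug mix happens to differ between arms, it can also move the arm means when need does not differ.

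**Working it through.** **1. Dose scales cited in section 3 (Justification).**

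| Drug | Dose cited | Use in the cited studies |
|---|---|---|
| Haloperidol, oral | 1.5 mg | prophylaxis |
| Haloperidol, IV | 2.5 mg/day: "administered 121 patients 2.5 mg of intravenous haloperidol daily" | prophylaxis |
| Olanzapine, oral | 5 mg | prophylaxis |
| Quetiapine | "The average dose used in these studies ranges from 40 mg to 200 mg" | treatment |
| Quetiapine, lower-dose studies | 25–40 mg/day | treatment |

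Raw ratios to haloperidol 2.5 mg:
- olanzapine 5/2.5 = 2
- quetiapine, lower doses: 25/2.5 = 10 to 40/2.5 = 16
- quetiapine, main range: 40/2.5 = 16 to 200/2.5 = 80

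The haloperidol and olanzapine figures are prophylaxis doses and the quetiapine figures are treatment doses. The ratios show that the scales differ. They are not equivalences.

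**2. Expected number of delirium cases.** The plan gives no figure for this variable, so the count comes from the sample size in section 6.3, which is reproduced first. With control risk 25%, absolute reduction 12 points (13% on quetiapine), two-sided 5% and 80% power:

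n = [1.96·√(2·0.19·0.81) + 0.842·√(0.25·0.75 + 0.13·0.87)]² / 0.12² ≈ 167 per arm

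With 5% losses, 167/0.95 = 175.8, so 176 against the stated 175.

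Cases with 175 per arm:
- control risk 20%: 175 × 0.20 = 35 on placebo and 175 × 0.08 = 14 on quetiapine
- control risk 25%: 175 × 0.25 ≈ 44 and 175 × 0.13 ≈ 23

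**3. Effect of pooling when both arms have the same drug mix.** Simulation with assumed inputs, since the documents give none: 43 and 23 cases, log-normal treatment need (log-SD 0.7), need 40% lower on quetiapine, and a share of cases on a drug whose milligram figure is 16 or 80 times larger for the same need. Power is for the Mann-Whitney test at 5%.

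| Share on the high-mg drug | Power, converted dose | Power, raw mg |
|---|---|---|
| 0% | 76–77% | 76–77% |
| 25% | 76–77% | 38–39% |
| 50% | 76–78% | 26–27% |

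Over the same ratios, the rank correlation between raw mg and true need is about 0.8 at a 10% share, 0.63 at 25% and 0.5 at 50%. When need is equal and both arms have a 25% share, the false-positive rate stays at or below 5%.

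**4. Effect when the mix differs between arms.** With equal need and shares of 20% and 30%, false positives are about 10–11% (Mann-Whitney) and 12–13% (t test). With 20% and 40% they are about 26–28% and 29–31%.

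A small example shows how the mean behaves. Assume each case needs either 4 mg of haloperidol or 100 mg of another agent. With 20% on the latter, the mean is 0.8·4 + 0.2·100 = 23.2 mg, of which 20/23.2 = 86% comes from that fifth. With 30%, the mean is 0.7·4 + 0.3·100 = 32.8 mg, which is 32.8/23.2 = 1.41 times as high. The median is 4 mg in both arms. With 44 and 23 cases (9 and 7 on the 100 mg agent), both tests give p = 0.37.

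**The case against.** - **Addition is not spelled out.** The text says haloperidol or another drug, and the CRD keeps drug, dose and route apart, so a report by drug is a possible reading. This stands in part. But a single total with one unit, matched to an objective over several antipsychotics, most naturally means pooling, and no other construction is given.
- **Mixing may be limited.** Section 3 calls haloperidol the first choice and the trial has one centre. This stands: the documents show that cases may receive different drugs, not that they will. Still, section 3 also describes side effects and non-response that limit haloperidol, and section 7.3 sets no restriction.
- **Blinding makes a systematic difference in drug mix unlikely.** This stands. A reader might infer that drug choice alone could make the comparison significant or reverse it. The documents give no reason to expect different mixes under identical capsules. With equal mixes the error rate is held, and the 20% against 30% example is far from significant. Section 10 also allows medians and a rank test, which protect against a few large values but do not recover the lost power.
- **The variable is minor.** It sits under an objective that describes delirium cases, and section 8.1 omits it from its efficacy list. This stands, and it limits the weight of the point.

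**Conclusion.** The point holds as a defect in how one secondary variable is measured. As worded, B.4 pools raw milligrams over drugs and routes that are not on a common scale, and nothing elsewhere corrects this. To the extent that cases receive different drugs or routes, the total reflects drug choice as well as need.

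The likely cost is noise: under the stated assumptions, power roughly halves when a quarter of cases receive a high-milligram drug. A chance difference in mix could also distort the arm means. The drug shares, spread of need, milligram ratio and 40% effect are all assumptions. If nearly every case receives haloperidol by one route, the effect is small.

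A reader might go further and infer that the total is meaningless, or that one quetiapine-treated case counts as much as 40 haloperidol-treated ones (100/2.5). The documents do not support either. Raw milligrams still carry information on need, and that ratio sets a treatment dose chosen from within a range against a prophylaxis dose. The primary endpoint and the sample size are unaffected.

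**What to change.** Change the wording in sections 1.14, 5.1 and 10:

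1. Do not pool raw milligrams across drugs.
2. Compare by arm the proportion given any rescue antipsychotic (yes/no), among all randomised patients. This avoids restricting the comparison to delirium cases, a group formed after randomisation.
3. If a total dose is compared, express it in haloperidol equivalents from one conversion table that covers route, named before unblinding.
4. Report dose by drug and route descriptively only. Testing haloperidol dose among haloperidol recipients would condition on a further choice made after randomisation.

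The cost is small. Drug, dose and route are already recorded in the CRD, so no new data are needed and no rescue treatment changes. The downside is that any conversion table is approximate and must come from outside the protocol.
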